### Exhibit B 2. SAS Code to Compute the M Estimates of Treatment Effect

---

```

*** derive primary and other endpoints;
data &OUTDAT2.;
  set &OUTDAT.;
  DELT_HB3 = HB_3 - HBBL;
  DELT_HB4 = HB_4 - HBBL;
  if (STRAT3 eq "US" and 10 le DELT_HB3 le 11) or
    (STRAT3 ne "US" and 10 le DELT_HB3 le 12) then
    HBRNGS3="Yes";
  else HBRNGS3="No";
  if (STRAT3 eq "US" and 10 le DELT_HB4 le 11) or
    (STRAT3 ne "US" and 10 le DELT_HB4 le 12) then

```

---

---

```

        HBRNGS4="Yes";
    else HBRNGS4="No";
run;
proc genmod data=&OUTDAT2.;
    by _IMPUTATION_
    class TRT (ref="DARB") STRAT1 STRAT2 ;
    model DELT_HB3=HB_BL STRAT1 STRAT2 TRT
        / alpha=0.05 cl diagnostics residuals ;
    estimate "Primary Efficacy" TRT 1 -1;
    lsmeans TRT / cl pdiff cov;
    ods output diffs = MI_ESTIMATES lsmeans=MI_ESTIMATES2;
run;

```

---

The execution of the above set of SAS code will provide the datasets MI\_ESTIMATES and MI\_ESTIMATES2 which will contain M lines of data that include the estimates and standard errors for each imputed dataset. The final result is then obtained with application of PROC MIANALYZE provided in [Exhibit B 3](#).

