## 2.3 Target Hb Ranges

In several places, this SAP refers to the following target Hb ranges as specified in the 2 protocols:

- US target: 10-11 g/dL
- EU, ROW target: 10-12 g/dL

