#### 6.3.2 Endpoints Related to Hb

The following efficacy endpoints are related to Hb:

- Change in average Hb value between Baseline and the combined PEP and SEP (Weeks 24 to 52)
- Having average Hb value in the geography-specific target range in Weeks 24 to 36 (yes/no variable)
- Having average Hb value in the geography-specific target range in Weeks 40 to 52 (yes/no variable)
- Having at least 1 Hb value in the geography-specific target range in Weeks 24 to 36 (yes/no variable)

Statistical Analysis Plan AKB-6548-CI-0014 and AKB-6548-CI-0015

- Having at least 1 Hb value in the geography-specific target range in Weeks 40 to 52 (yes/no variable)
- Having Hb values in the geography-specific target range for at least 1/2 of the observations in Weeks 24 to 36 (yes/no variable)
- Having Hb values in the geography-specific target range for at least 1/2 of the observations in Weeks 40 to 52 (yes/no variable)

These endpoints apply only to study CI-0014:

- Hb increase of >1.0 g/dL from Baseline to Week 52 (yes/no variable)
- Time to achieve Hb increase of >1.0 g/dL from Baseline Hb (censored at Week 52)

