## 9.3 Other Efficacy Endpoints: Strategies for Analysis

The study has many other efficacy endpoints. Because of their exploratory nature, they will not be corrected for multiplicity.

### 9.3.1 Having Average Hb Value in the Geography-Specific Target Range in Weeks 24 to 36

All subjects will be defined as either being in their geography-specific target range (see [Section 2.3](#)) in Weeks 24 through 36 (“yes”) or not (“no”), based on the average Hb value during the four visit windows in Weeks 24 through 36. Subjects with no Hb value in the PEP value will be treated as missing and handled according to [Appendix B](#).

The proportion of subjects within target range will be calculated and tested with a Mantel-Haenszel test stratified by the baseline strata. See [Appendix B](#) and [Appendix D](#).

Noninferiority will be evaluated using a 2-sided confidence interval for the difference in proportions. Noninferiority will have been established if the lower limit of the confidence interval is above -15%. The power for this endpoint is expected to be roughly 90%.

If the lower limit of the 2-sided confidence interval for the difference in proportions is above zero, superiority will have been established and the finding will be interpreted as providing evidence of a higher proportion of subjects being within the target range for vadadustat relative to the control arm.

### 9.3.2 Having Average Hb Value in the Geography-specific Target Range in Weeks 40 to 52

All subjects will be defined as either being in their geography-specific target range (see [Section 2.3](#)) in Weeks 40 to 52 (“yes”) or not (“no”), based on the average Hb value during the Weeks 40 to 52 visit windows. Subjects with no Hb value in the SEP value will be treated as missing and handled according to [Appendix B](#).

The proportion of subjects within target range will be calculated and tested with a Mantel-Haenszel test stratified by the baseline strata. See [Appendix D](#).

Noninferiority will be evaluated using a 2-sided confidence interval for the difference in proportions. Noninferiority will have been established if the lower limit of the confidence interval is above -15%. The power for this endpoint is expected to be roughly 90%.

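### SAP Exhibit B 2 tests the change in Hb, not Hb itself, against the 10-11 and 10-12 g/dL target limits, so both average-Hb target-range endpoints come out as No for every subject

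*SAP*

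**What the plan says.** **Definitions in the text.** SAP Section 2.3 gives the targets as Hb levels: 10-11 g/dL in the US and, elsewhere, "EU, ROW target: 10-12 g/dL". Section 9.3.1 classifies each subject as in range or not "based on the average Hb value during the four visit windows in Weeks 24 through 36", and Section 9.3.2 does the same for Weeks 40-52. Table B 1 lists the flags `HBRNGS3` and `HBRNGS4` as outcomes of the period Hb variables. Each endpoint has its own decision rule, "Noninferiority will have been established if the lower limit of the confidence interval is above -15" (in percentage points), followed by a superiority reading if the lower limit is above zero. On status, Section 9.3 says of the other efficacy endpoints: "Because of their exploratory nature, they will not be corrected for multiplicity".

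**Code.** Exhibit B 2 sets "DELT_HB3 = HB_3 - HBBL" and defines `DELT_HB4` likewise. Its next statement is "if (STRAT3 eq 'US' and 10 le DELT_HB3 le 11) or", with 10-12 for non-US subjects; meeting either condition gives Yes and anything else gives No. The pair is repeated on `DELT_HB4`. The output dataset `&OUTDAT2` is the one that Exhibit B 5 analyses with the Mantel-Haenszel risk difference.

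**Standing of the code.** Section 1 presents the code as stating exactly what each analysis is meant to be. Appendix B.1 says the code and its seeds will produce the analysis datasets. Appendix B.2 foresees slight modification for software versions and fit to the data, and the Table B 1 footnote calls the variable names preliminary.

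**The concern.** A limit expressed as an Hb level is applied to a difference between two Hb values. Every definition in the SAP's text points to the period average; only the code departs from it. If the exhibit is programmed as written, the two endpoints have no responders in either arm, and their noninferiority and superiority statements rest on 0% against 0%.

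The error would most likely surface after unblinding, when the table is first produced. Correcting an endpoint derivation at that point is harder to defend than correcting it before lock. Protocol Section 5.3 (Amendment 7-COL) also lists target-range proportions for these two periods as key secondary endpoints, although the SAP states that its own methods prevail.

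The same exhibits contain loose ends that belong in the same edit. None is shown to make the primary result wrong.

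- **Region.** It is `STRAT3` in the Exhibit B 2 range test, `STRAT3_REG` in Exhibit B 1, `STRAT1` in Appendix C.1.1 and `STRAT2A` in Table B 1.
- **Baseline Hb.** The data step subtracts `HBBL`, but the model statement is "model DELT_HB3=HB_BL STRAT1 STRAT2 TRT".
- **Pooling step.** Exhibit B 3 names `MI_ESTIMATES2` first, with `MI_ESTIMATES` as an alternative. The first holds arm LS means; the text below it needs the difference.

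**Working it through.** The plan states no figure that depends on this code, so there is none to reproduce. The check is what the code returns.

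**Inputs**
- Eligible mean screening Hb: 8.0-11.0 g/dL in the US, 9.0-12.0 elsewhere (Protocol Section 7.2).
- SD of the change: 1.5 g/dL, equal mean change in both arms (SAP Section 2.7). Taking that mean as 0 is my assumption; +1 and +2 are shown as alternatives.
- 925 subjects per arm, so 1,850 (SAP Section 2.6); M = 100 imputations (Appendix B.1).

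**Step 1: Hb needed for Yes.** The change must be at least 10.
- US: from 8.0 + 10 = 18 up to 11.0 + 10 = 21 g/dL, depending on the starting value.
- Non-US: from 9.0 + 10 = 19 up to 12.0 + 10 = 22 g/dL.

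These bounds are approximate, because SAP Section 9.1.1 takes baseline as the average of the last two central values up to first dose, not the screening mean.

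**Step 2: probability.** z = (10 - 0)/1.5 = 6.67.

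| Mean change (g/dL) | Probability per record | Expected Yes in 1,850 × 100 = 185,000 records |
|---|---|---|
| 0, limits 10-11 | 1.30 × 10^-11 | 2.4 × 10^-6 |
| 0, limits 10-12 | 1.31 × 10^-11 | 2.4 × 10^-6 |
| +1, limits 10-12 | 9.9 × 10^-10 | 1.8 × 10^-4 |
| +2, at least 10 | 4.8 × 10^-8 | 8.9 × 10^-3 |

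**Step 3: emulation of the data step.** Assumptions: baseline uniform over the eligible range, half the subjects US, change normal with mean 0 and SD 1.5. Over 185,000 records the code as written gave no Yes, and the largest change was 7.1 g/dL. If `HBBL` is not in the dataset, the change is missing, both conditions fail, and the flag is again No.

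**Step 4: downstream.** With 0% in each arm in every imputation, the risk difference is 0 with no within- or between-imputation variance. The -15% criterion is then either met trivially or undefined.

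**Step 5: with the right variable.** Under the Step 3 assumptions (200,000 simulated subjects), testing `HB_3` gives about 31% Yes: 19% US and 42% non-US. If `STRAT3` did not hold region, every subject would be judged against 10-12, and the US share would read about 31% instead of 19%. These percentages are illustrative, not predictions.

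**Step 6: pooling input.** Take arm LS means of 0.10 (vadadustat) and 0.30 (darbepoetin alfa), M = 100, SD 1.5 and 925 per arm.
- `MI_ESTIMATES` (100 rows): -0.20 (95% CI -0.34 to -0.06), the treatment difference.
- `MI_ESTIMATES2` (200 rows): 0.20 (-0.02 to 0.42), an average of the two arms.

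**The case against.** The best case against this is that no one could misread the endpoint. Sections 2.3, 6.3.2 and 9.3 and Table B 1 all describe an Hb level, and Appendix B.1 has the continuous value imputed before any change score or binary flag is derived. Appendix B.2 refers to the listings as examples. They could not run unaltered in any case: Exhibit B 2 lacks a semicolon after its BY variable, the last FCS statement in Exhibit B 1 lacks one, and the STDERR statement in Exhibit B 3 names no variable. A programmer must therefore rewrite them. The endpoints are exploratory, and a table with no responders would be questioned at once. The names are declared preliminary, and the text under Exhibit B 3 already says that the difference is what counts.

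Much of this stands, and it limits the weight of the point. It is a coding slip, the primary and secondary endpoints properly use the change score, and a plausible but wrong result is unlikely. The emulation also treats imputed records as independent although imputations share their observed values, so the maximum of 7.1 g/dL says little; the expected counts do not depend on independence.

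It does not remove the error. Appendix B.1 commits to generating the datasets with this code. An allowance for software, data compatibility or renaming does not extend to replacing the variable that defines an endpoint. Syntax slips elsewhere do not make the range test right, and nothing in the SAP says whether its text or its code governs when they differ.

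**Conclusion.** The concern holds. As written, Exhibit B 2 classifies essentially every subject as out of range in both periods: under 0.01 expected Yes flags in 185,000 records even at an assumed mean change of +2 g/dL with SD 1.5. The two average-Hb target-range analyses would be uninformative.

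The scope is narrow. The four other target-range endpoints (at least one value, at least half of the values) use observed Hb according to Table 3 and do not pass through this code. The range error leaves the primary and the single secondary endpoint unchanged. The baseline-name mismatch could leave the primary outcome variable empty if only `HB_BL` exists, but that would be an evident run failure, not a bias. This should be fixed before lock; it does not threaten the trial's main conclusion.

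**What to change.** In the four range conditions of Exhibit B 2, replace `DELT_HB3` with `HB_3` and `DELT_HB4` with `HB_4`. Keep the change scores for the primary and secondary models. In the same revision:

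- Use one set of stratification names across Table B 1, Exhibits B 1, B 2 and B 5, and Appendix C. The range test must read region, and the primary model must contain region and NYHA class, as Section 9.1.4 requires.
- Use one name for baseline Hb, either `HBBL` or `HB_BL`.
- In Exhibit B 3, name only `MI_ESTIMATES`, the differences dataset, for the primary test.
- Repair the missing semicolons and the incomplete STDERR statement.

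The cost is a few lines of SAP code. No data, sample size or endpoint definition changes, and the edit is best made before database lock and unblinding.

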### **Exhibit B 3. SAS Code to Obtain the Overall Estimate and Standard Error**

---

```

proc mianalyze data= MI_ESTIMATES2 (or MI_ESTIMATES);
    modeleffects estimate;
    stderr;
    ods output ParameterEstimates=MI_PRIMARY;
run;

```

---

The final results will be contained in the output dataset MI\_primary. This dataset will contain the 95% confidence limits of the difference. The primary hypothesis is tested by comparing the lower limit of this confidence interval to -0.75 g/dL.

#### **B.3.2. Tipping Point Sensitivity Analysis for Missing Data**

This multiple imputation model for the primary efficacy model described above assumes that data in both treatment arms are missing at random (MAR) and would therefore follow the trend of observed data. The tipping point analysis assesses the effect of potential deviations from this assumption and explores the consequences of assuming that data in the vadadustat arm are missing not at random (MNAR) (i.e., subjects in the vadadustat arm with missing outcome are assumed to have a lower Hb values than subjects in the darbepoetin alfa arm). The specific steps are as follows:

Statistical Analysis Plan AKB-6548-CI-0014 and AKB-6548-CI-0015

- A. The missing information on Hb in the vadadustat arm will be multiply imputed using a shift parameter S applied to lower the mean Hb values in that arm. The sample SAS code for performing multiple imputation with a shift S in the vadadustat arm is presented in [Exhibit B 4](#). Missing data in the darbepoetin alfa arm will continue to be imputed assuming MAR, using the same code as for the primary efficacy analysis subset to the darbepoetin arm.
- B. The multiply-imputed data will be analysed using standard multiple imputation combining rules to obtain an estimated treatment effect and its associated 95% confidence interval. These analyses provide a realistic estimate of variance for the treatment effect that takes into account the uncertainty caused by the missing data.
- C. Steps A and B will then be repeated. The shift parameter S starts from 0, which corresponds to the primary efficacy analysis with no shift effect, and increased in the negative direction by a certain amount in each step until the analysis reaches the “tipping point”, the point at which the effect of vadadustat is no longer noninferior to that of darbepoetin alfa. The more the tipping point diverges from the observed data, the more robust the conclusion based on primary efficacy analysis.

The tipping point analysis will use a single seed from [Listing B 1](#) to generate however many seeds are needed, i.e., 1 per treatment group per shift.

#### **Exhibit B 4. SAS Code for Tipping Point Analysis**

---

```
proc mi data=&INDAT. (where=(TRT="VADA")) nimpute=&M.
    seed=&SEED2. out=&OUTDAT.;
class &BINVARS. &NOMVARS. &ORDVARS.;
var
    STRAT2_HF STRAT3_REG
    SEX RACE AGE HX_CV4 HX_CV_OTH HX_DM ESA_BL SMOKE_BL
    HEP_BL FERR_BL TIBC_BL CRP_BL TSAT_BL HB_BL
    HB_1 HB_2 HEP_3 FERR_3 TIBC_3 CRP_3 TSAT_3 HB_3
    HB_4;
fcs reg ( HB_3) nbiter=40;
mnar adjust ( HB_3 / shift=&S. );
run;
```

---

#### **B.4. Secondary Efficacy Analyses**

The secondary endpoint, change in Hb at Time 4, is continuous and will be analyzed in a manner similar to the method to be used for the primary efficacy analysis.

#### **B.5. Other Efficacy Analyses**

For the below 2 efficacy endpoints of having average Hb value in the geography-specific target range in weeks 24-36 and having average Hb value in the geography-specific target range in weeks 40-52, their endpoints are binary; they will be analyzed according to the Mantel-Haenszel estimate of stratified risk differences. These binary outcome measures will be computed from the continuous imputed data which will serve as the input data set for the computation of the estimate of risk difference. The code for this analysis is provided in Exhibit B 5. Rubin’s rule requires that the input statistic is normally distributed, which we assume for this estimate.

---

**Exhibit B 5. SAS Code to Obtain the Mantel-Haenszel Estimate of Risk Difference**

---

```

*** compute the MH estimate;
proc freq data=&OUTDAT2.;
  by _IMPUTATION_;
  tables STRAT1*STRAT2*STRAT3*TRT*&OUTCOME/riskdiff(common) cmh;
  ods output CommonPdiff=CommonPdiff;

run;

*** combine the results;
proc mianalyze data= CommonPdiff;
  modeleffects Value;
  stderr;
  ods output parameterestimates=MI_SEC;

run;

```

---

Multiple imputation is not currently planned for the other efficacy analyses, except in the case that outcomes for these analyses are part of the multiple imputation for the primary efficacy analysis. If analysis of a covariate included in the overall imputation model (Table B 1) is desired, follow the procedure for the primary or secondary analyses, depending on the variable type.

### B.6. Random Seed Specification

This section presents the generation code, resulting random seeds, and corresponding analysis assignments for all analyses with multiple imputation. The random seeds for all the multiple imputation runs for each trial will be generated from a single master seed. The master seeds will be 10014 for CI-0014, and 10015 for CI-0015.

---

**Exhibit B 6. SAS Code for Random Seed Generation**

---

```

data SEED;
  call streaminit(&MASTER.);
  do I = 1 to &NUMSEED. ;
    SEED = put(ceil( ((2**31) - 1) * rand("UNIFORM") ), best.);
    output;
  end;
run;

```

---

The seeds and their analysis assignments are shown in [Listing B 1](#). These will be used for all imputations required in both efficacy and MACE safety analyses for this set of trials.

Statistical Analysis Plan AKB-6548-CI-0014 and AKB-6548-CI-0015

**Listing B 1. Random Seed Assignment for all Planned Analyses**

| Analysis Category                            | Analysis ID | Analysis Detail                          | PRO 2 TECT |                      | INNO 2 VATE |                      |
|--|-------------|--|-----------------------|----------------------|------------------------|----------------------|
|  |             |  | CI-0014 a  | CI-0015 b | CI-0016 c   | CI-0017 d |
| Primary Efficacy, Secondary, & All Subgroups | PE          | Impute missing Hb & covariates           | 635320903             | 1987393372           | 32552474               | 1864814524           |
| Primary Efficacy - Sensitivity               | PES1        | Rescue definition 1 (narrow)             | 429585122             | 1373196336           | 1027066416             | 928246872            |
|  | PES2        | Rescue definition 2 (broad-on-treatment) | 549618248             | 1156395436           | 477818637              | 2071955541           |
|  | PES3        | Tipping point                            | 340408944             | 1747908400           | 1450082522             | 216479710            |

Analyses that use a shared seed between CI-0014 and CI-0015 or CI-0016 and CI-0017 are highlighted in yellow.

a. Seeds for CI-0014 are generated based on a master seed of 10014.

b. Seeds for CI-0015 are generated based on a master seed of 10015.

c. Seeds for CI-0016 are generated based on a master seed of 10016.

d. Seeds for CI-0017 are generated based on a master seed of 10017.

## APPENDIX C. ANALYSIS OF CONTINUOUS ENDPOINTS

This appendix provides details related to the analysis of the continuous endpoints in the studies. It includes a description of the statistical approaches and provides examples of the SAS code for the analysis of specific continuous endpoints. The primary efficacy analysis will be an analysis of covariance (ANCOVA) with multiple imputation for missing data based on standard imputation. The details of this approach are provided in [Appendix B](#).

Additional analyses will use the ANCOVA method including some sensitivity analyses for the primary efficacy endpoint, secondary efficacy endpoint analyses, and other continuous exploratory endpoint analyses. Other sensitivity analyses for the primary efficacy endpoint will use a mixed model repeated measures (MMRM) without imputing missing data.

### C.1. Analyses using ANCOVA

#### C.1.1. Primary Analysis

The primary analysis is based on the change in average Hb between the baseline and the primary efficacy period (PEP), Weeks 24 to 36. The noninferiority analysis will be based on a margin of -0.75 g/dL applied to the mean change in vadadustat minus darbepoetin alfa. To establish noninferiority, the lower limit of the confidence interval of the mean change in vadadustat minus darbepoetin alfa must be -0.75 g/dL or higher. If the lower limit of the 2-sided 95% confidence interval for the difference between the mean in the vadadustat group and the mean in the darbepoetin alfa group is above zero, superiority will have been established and the finding will be interpreted as providing evidence of a greater change from baseline in Hb for vadadustat relative to the control arm.

The primary efficacy analysis is based on the estimated confidence interval estimated from an ANCOVA model. The computation of this confidence interval is described in this section. Modifications for additional continuous endpoints are outlined in a separate section.

The ANCOVA model will be fit using PROC GENMOD in SAS with the following variables:

- HB\_BL – this is the average of the last 2 Hb measure on or prior to the first dose date
- DELT\_HB3 – this is computed as the average Hb measure computed from the PEP (Week 24 to 36) visits minus HB\_BL
- TRT – denotes treatment group; vadadustat or darbepoetin alfa
- STRAT1 – stratification factor of geographic region (US, EU, versus Rest of World)
- STRAT2 – NYHA CHF class 0 or I versus II or III

The basic SAS code to fit the model is in [Exhibit C 1](#), but the full process includes multiple imputed datasets as seen in [Exhibit B 2](#).

### Exhibit C 1. SAS Code for Primary Analysis

---

```
proc genmod data=&OUTDAT2.;
    class TRT (ref="DARB") STRAT1 STRAT2 ;
    model DELT_HB3=HB_BL STRAT1 STRAT2 TRT
        / alpha=0.05 cl diagnostics residuals ;
    estimate "Primary Efficacy" TRT 1 -1;
    lsmeans TRT / cl pdiff cov;
    ods output diffs = MI_ESTIMATES lsmeans=MI_ESTIMATES2;

run;
```

---

The confidence limits for the coefficient associated with TRT in the above model are used to compute the confidence intervals based on M imputed datasets.

#### C.1.2. Select Sensitivity Analyses for the Primary Efficacy Endpoint

To assess the robustness of the primary efficacy analysis, the sensitivity analyses outlined below will be conducted using the same method in the primary efficacy analysis, but starting from different missing data patterns, imputation models, or analysis populations. As with the primary analysis, the following sensitivity analyses will use multiple imputation and ANCOVA.

- The primary analysis will be repeated after setting to missing all per-visit hemoglobin values within four weeks of administration rescue therapy. The definition of rescue therapy will vary across the series described in [Section 6.3.9](#).
- Tipping point analyses (see [Appendix Section B.3.2](#)) will be performed to assess the effect of the missing data.
- The Full Analysis Set (FAS) population will be used instead of the randomized population. This analysis will be performed only if the size of the FAS is less than 95% of the randomized population.

